6.4 Coagulopathy

If symptomatic, omit Day 9 asparaginase and consider factor replacement (FFP, cryoprecipitate, factor VIIa). Do not hold asparaginase (*Erwinia*) for abnormal laboratory findings without clinical symptoms.

6.5 Hepatic Toxicity

6.5.1 Transaminases:

If the ALT or AST are > 10 x ULN, attempts should be made to identify the cause and notify the Study Chair. In most cases, the therapy will proceed without modification.

6.5.2 Hyperbilirubinemia:

If the direct bilirubin is > 3 mg/dL, notify the Study Chair. In some cases, it may be necessary to proceed if the bilirubin elevation is a result of the leukemia itself. If the elevated direct bilirubin is not a result of the leukemia, modify the doses of daunorubicin, etoposide and mitoxantrone as follows below. For all cases in which the direct bilirubin is elevated at the point in time that the next course is to begin, consider delaying the course for 1 week to determine whether the direct bilirubin falls to an acceptable level.

6.5.3 Asparaginase:

L-asparaginase has been associated with hepatic toxicity but dosing guidelines for hepatic toxicity are not available. Thus, asparaginase administration in the setting of hepatic toxicity is at the clinician's discretion.

6.5.4 Daunorubicin, Etoposide and Mitoxantrone:

In severe liver dysfunction, the half-life of mitoxantrone is prolonged and the AUC may be more than 3-fold that of patients with normal hepatic function. However,

there are no available dose adjustment guidelines in the literature. Therefore, similar dose reductions of mitoxantrone as outlined below for daunorubicin are utilized on this protocol.

Direct Bilirubin	Daunorubicin	Etoposide	Mitoxantrone
≥ 2 and < 3 mg/dL	50% of the calculated dose	50% of the calculated dose	50% of the calculated dose
≥ 3 and < 5 mg/dL	25% of the calculated dose	25% of the calculated dose	25% of the calculated dose
≥ 5 mg/dL	Hold dose and notify study chair	Hold dose and notify study chair	Hold dose and notify study chair

Full dose of daunorubicin, etoposide and mitoxantrone may resume when the direct bilirubin has fallen to < 1.2 mg/dL.

6.6 Neurologic Toxicity

6.6.1 Cytarabine:

Patients with $>$ Grade 3 CTCAE v 5.0 nervous system disorders from high dose cytarabine should not receive further high dose cytarabine. The most common nervous system disorder is an acute cerebellar syndrome that may manifest itself as ataxia, nystagmus, dysarthria, or dysmetria. However, seizures and encephalopathy have also occurred following therapy with high dose cytarabine.

6.7 Pancreatitis

6.7.1 Asparaginase

Discontinue asparaginase (*Erwinia*) in the presence of hemorrhagic pancreatitis or severe pancreatitis (abdominal pain $>$ 72 hours and $>$ Grade 3 amylase elevation ($> 2.0 \times$ ULN)). In the case of mild pancreatitis after Day 2, Day 9 asparaginase may be given only if symptoms and signs subside, and amylase levels return to normal. Severe pancreatitis is a contraindication to additional asparaginase administration.

6.8 Renal Toxicity

6.8.1 Cytarabine:

Patients with nephrotoxicity secondary to antibiotics, or antifungals, may have prolonged excretion of cytarabine leading to more severe marrow and extramedullary toxicity. Patients with a serum creatinine > 2 mg/dL or $> 2 \times$ normal for age should be hydrated orally or intravenously. Following hydration, the patient must have a creatinine clearance ≥ 60 mL/min/1.73m² as measured preferably by a nuclear GFR Scan or timed urine collection for creatinine clearance before proceeding with high dose cytarabine therapy (doses of 1,000 mg/m² or greater). If the CrCl is abnormal (< 60 mL/min/1.73m²) then high dose cytarabine should be reduced from twice daily to once daily dosing, at the same previously prescribed doses (e.g., 50% daily dose reduction). With this approach, previous research has shown the prevention of subsequent neurotoxicity in recipients of high dose cytarabine in the face of renal insufficiency.

6.8.2 Etoposide:

In patients with impaired renal function, the following **initial** dose modification of etoposide should be considered based on measured creatinine clearance:

- for CrCl > 60 mL/min, give full dose,
- for CrCl of 15 – 60 mL/min, give 75% of the dose (25% dose reduction).

- for CrCl < 15 mL/min, notify the Study Chair.

(Please note: For dose adjustment in renal dysfunction for children, use the “corrected” value for creatinine clearance measured in mL/min/1.73 m², which ‘corrects’ that value for the standardized values of CrCl in adults is measured in mL/min. The “corrected” value is loosely interpreted as being equivalent to creatinine clearance measured in an adult patient). **Subsequent doses** should be based on patient tolerance and clinical effect.

6.9 Thrombosis

6.9.1 Asparaginase

Discontinue asparaginase and treat with appropriate antithrombotic therapy, as indicated. Do not hold asparaginase for abnormal laboratory findings without clinical sequelae. For significant thrombosis, not line related, consider evaluation for inherited predisposition to thrombosis.

6.10 Sinusoidal Obstruction Syndrome (SOS, formerly VOD) of the Liver

6.10.1 Gemtuzumab Oozagamicin (GO)

SOS is a known toxicity of GO. No specific predisposing factor is known that may identify the patient at risk.

Criteria for the diagnosis of SOS of the liver

For the purposes of reporting toxicity, the following definition for SOS will be used:

- 1) Weight gain of more than 10% baseline, and
- 2) Right upper quadrant pain or tender hepatomegaly, and
- 3) Total bilirubin 2 mg/dL or greater, and
- 4) Edema or ascites.

Reversal of portal venous blood flow by ultrasound or pathologic confirmation by liver biopsy are not required for the diagnosis but may be done in support of the clinical diagnosis and/or the evaluation of other diagnostic possibilities. Ultrasound may also be used to assess the severity and course of the patient’s SOS.

6.11 Palmar-Plantar Erythrodysesthesia Syndrome, Skin Pain that impacts ADLs or Rash Maculo-Papular

6.11.1 Sorafenib

Grade 1 – Continue sorafenib with topical therapy and supportive care*

Grade 2

- First occurrence – hold sorafenib, if rash improved to <grade 2 in 2 weeks, restart at same dose. If does not improve in 2 weeks, hold till rash improves then start drug at 100 mg/m²/day dose.
- Second occurrence – hold sorafenib, if rash improved in 2 weeks, restart at 100 mg/m²/day dose. If does not improve to <grade 2 in 2 weeks, stop sorafenib
- Third occurrence – stop sorafenib

Grade 3

- First occurrence – hold sorafenib, if rash improved in 2 weeks, restart at 100 mg/m²/day dose. If does not improve to <grade 2 in 2 weeks, stop sorafenib
- Second occurrence – stop sorafenib

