6.0 DOSE MODIFICATION FOR TOXICITIES

Common Terminology Criteria for Adverse Events (CTCAE)

The descriptions and grading scales found in the revised NCI Common Terminology Criteria for Adverse Events (CTCAE) version 5.0 will be utilized for AE reporting. All appropriate treatment areas should have access to a copy of the CTCAE version 5.0. A copy of the CTCAE version 5.0 can be downloaded from the CTEP website (<http://ctep.cancer.gov>).

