NERVOUS SYSTEM DISORDERS		
	Dizziness	
	Headache	
		Intracranial hemorrhage
		Reversible posterior leukoencephalopathy syndrome
PSYCHIATRIC DISORDERS		
	Insomnia	
RENAL AND URINARY DISORDERS		
	Acute kidney injury	
RESPIRATORY, THORACIC AND MEDIASTINAL DISORDERS		
	Cough	
	Dyspnea	
	Respiratory hemorrhage	
	Voice alteration	
SKIN AND SUBCUTANEOUS TISSUE DISORDERS		

Adverse Events with Possible Relationship to Sorafenib (BAY 43-9006; Nexavar) (CTCAE 4.0 Term) [n= 2571]		
Likely (>20%)	Less Likely (<=20%)	Rare but Serious (<3%)
Alopecia		
	Dry skin	
		Erythema multiforme
Palmar-plantar erythrodysesthesia syndrome		
	Pruritus	
Rash maculo-papular		
		Stevens-Johnson syndrome
		Toxic epidermal necrolysis
VASCULAR DISORDERS		
	Hypertension	
		Thromboembolic event

Formulation and Stability:

Sorafenib is supplied as a yellow-orange 50 mg and a red-colored 200 mg, round, immediate-release filmcoated tablet containing the excipients croscarmellose sodium, microcrystalline cellulose, hydroxypropylmethylcellulose, sodium lauryl sulfate, and magnesium stearate. The 200 mg film-coat consists of hydroxypropylmethyl cellulose, polyethylene glycol, titanium dioxide and red iron oxide. The 50 mg film-coat consists of hypromellose, PEG 3350, titanium dioxide, and yellow ferric oxide. The film coating has no effect on active BAY 43-9006 tosylate release rate.

Sorafenib 200 mg tablets are supplied in high-density polyethylene (HDPE) bottles of 140 tablets and the 50 mg tablets are supplied in HDPE bottles of 100 tablets. The bottles should be stored at controlled room temperature (15-25°C; 59-77°F) and storage temperature should not exceed 25°C (77°F). Stability testing is ongoing.

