11.1 STATISTICAL CONSIDERATIONS

Sample size: This is a pilot study aimed at utilizing a risk-stratified approach along with pharmacogenomics to treat newly diagnosed patients with AML. Annually we expect to have 10-20 de novo AML patients to be diagnosed and treated at our institution. This two-year study would be expected to enroll approximately 30 patients (both low and high risk) during that time period. As a pilot study, this trial is not hypothesis-driven but rather estimation-driven, and the sample size is based on a feasible two-year target for our institution.

Descriptive statistics will be conducted for demographic and patient characteristic variables, including toxicity related variables. Mean and standard deviation will be used for continuous variables and frequency and percent will be used for categorical variables.

Primary Endpoints:

1. Event-free survival: Event-free survival (EFS) is defined as the time from on study to death, failure to achieve remission or relapse, where those patients who do not experience these events will be censored at last follow-up date. EFS will be estimated using the Kaplan-Meier method for newly diagnosed patients with pediatric acute myeloid leukemia using a risk stratified approach.

Secondary Endpoints:

1. Disease-free survival: Disease-free survival (DFS) from end of first course of therapy is defined as time from end of first course of therapy to death or relapse, where those patients who do not experience these events will be censored at last follow-up date. DFS will be estimated using the Kaplan-Meier method for newly diagnosed patients with pediatric acute myeloid leukemia using a risk stratified approach.
2. Overall survival: Overall survival (OS) is defined as (1) time from study entry and (2) from end of first course of therapy to death, where those who do not die will be censored at

last follow-up date. OS will be estimated using the Kaplan-Meier method for newly diagnosed patients with pediatric acute myeloid leukemia using a risk stratified approach.

3. Minimal residual disease: Minimal residual disease (MRD) is the proportion of patients that are in remission (MRD negative) after one cycle of induction chemotherapy in both the GO and non-GO groups. Descriptive statistics (frequency and percent) will be used to estimate the frequency of MRD.

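### As worded, the sorafenib rule for a first Grade 3 skin reaction tells the clinician both to restart and to stop when the rash has fallen to Grade 2 at two weeks

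*Combined protocol and SAP*

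**What the plan says.** Section 6.11.1 of the protocol sets the sorafenib rules for hand-foot syndrome, skin pain that limits daily activities, and maculo-papular rash. For a first Grade 3 occurrence the drug is held, and two sentences then decide what follows: "if rash improved in 2 weeks, restart at 100 mg/m²/day dose. If does not improve to <grade 2 in 2 weeks, stop sorafenib". The first gives the restart condition and the second gives the stop condition. A second Grade 3 occurrence is an unconditional stop.

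The neighbouring Grade 2 bullets matter for the comparison. For a first Grade 2 occurrence the drug is held, and the restart condition does name a grade: "if rash improved to <grade 2 in 2 weeks, restart at same dose". Its companion sentence, for a rash that has not improved by then, prolongs the hold and names no grade. The bullet for a second Grade 2 occurrence uses the same pair of sentences as the one for a first Grade 3 occurrence. At Grade 1, sorafenib continues.

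On grading, section 6.0 says that the "Common Terminology Criteria for Adverse Events (CTCAE) version 5.0 will be utilized for AE reporting". It sets no restart threshold for skin events.

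**The concern.** A rule with two mutually exclusive actions needs conditions that divide the possible outcomes between them. Here one condition is improvement of any size and the other is failure to reach a fixed grade, so the two overlap wherever a rash has improved without getting below Grade 2. From Grade 3, that is a one-grade improvement, which is an ordinary course for a reaction under treatment.

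In that overlap the two instructions are opposites for the same child on the same day. One re-exposes the child to sorafenib while a Grade 2 reaction continues; the other ends sorafenib for good. Sections 5.2, 5.4, 5.6 and 5.8 schedule sorafenib in all four chemotherapy courses for FLT3-ITD patients, so the choice can carry into later courses. The reactions are also expected ones: the toxicity table in section 9.6 lists "Palmar-plantar erythrodysesthesia syndrome" and maculo-papular rash in its most frequent column (above 20%).

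**Working it through.** No sample size, power or error rate is involved, and the plan gives no figure to reproduce. The check is to apply the two sentences, as written, to each possible grade two weeks after a first Grade 3 event.

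| Grade at two weeks | Improved from Grade 3? (restart) | Not below Grade 2? (stop) | Instruction as worded |
|---|---|---|---|
| 0 or 1 | yes | no | restart only |
| 2 | yes | yes | restart and stop |
| 3 | no | yes | stop only |

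Exactly one outcome, Grade 2, meets both conditions. If the bare word in the restart sentence is read as improvement to below Grade 2, that row becomes stop only and the overlap disappears. The Grade 3 bullet does not contain that qualification.

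The same pair of sentences in the bullet for a second Grade 2 occurrence does much less harm. Starting from Grade 2, an improvement of a full grade is already below Grade 2, so the conditions clash only if improvement within Grade 2 is counted.

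I then looked for text that would settle the Grade 3 case.
- The supportive-care notes that follow section 6.11.1 cover topical and oral treatment only.
- Section 6.0 supplies the grading scale only.
- The unconditional stop at a second Grade 3 occurrence does not bear on the first.
- Sections 6.3.3 and 6.3.4 name restart levels for cardiac function and blood pressure, which shows that the protocol states such levels elsewhere, but they do not apply to skin.

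No passage defines improvement for skin toxicity or says which sentence takes precedence.

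For scale, the inputs from the documents are an FLT3 mutation frequency of about 15% (section 2.4) and enrolment of up to 30 (section 3.0):
- expected patients with FLT3 mutations: 0.15 × 30 = 4.5.

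Two further inputs are my assumptions, with no source in the documents: 10% to 30% of sorafenib patients reach Grade 3, and half of those are at Grade 2 after two weeks.
- Low: 4.5 × 0.10 × 0.5 = 0.225, about 0.2 patients.
- High: 4.5 × 0.30 × 0.5 = 0.675, about 0.7 patients.

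For one expected patient to meet the conflict, 1 / 4.5 = 22% of sorafenib patients would have to reach Grade 3 and then be at Grade 2 at two weeks. The high assumption gives 0.30 × 0.5 = 15%.

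The 4.5 is itself on the high side. The 15% refers to activating FLT3 mutations in general, section 2.4 reserves sorafenib for FLT3-ITD with an allelic ratio above 0.1, and 30 is a ceiling.

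**The case against.** The best answer is that section 6.11.1, read as a whole, points to a single threshold. Each of its three conditional bullets names the below-Grade-2 level exactly once and leaves it out of the paired sentence. The first Grade 2 bullet puts it in the restart sentence; the other two put it in the stop sentence. That pattern looks like compressed drafting with one threshold per bullet. In addition, Grade 2 is itself a reason to hold sorafenib in the same section, so restarting with a continuing Grade 2 reaction would sit awkwardly beside that rule.

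This stands as evidence of what may have been intended, and a reader should not infer that the section gives the clinician no guidance at all. It does not remove the contradiction. The threshold is left to inference in the one bullet where its absence changes the action, and nothing says whether a residual Grade 2 rash after a Grade 3 event counts as a Grade 2 occurrence.

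Two further objections are right. The trial is single-center (section 3.0), so a reader who imagines different sites applying different rules would be mistaken; any variation is between clinicians at one institution. And the patient count is soft: the frequency column in section 9.6 gives neither grade nor age group, so it cannot support a Grade 3 rate.

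**Conclusion.** The rule for a first Grade 3 skin event is contradictory as worded, for one outcome only: a fall to Grade 2 at two weeks. That conclusion rests on the literal text and needs no assumption about rates. The size is small. An expected 4 to 5 of 30 patients, at most, would have FLT3 mutations, and probably fewer than one would reach the conflict, on assumptions that serve only as illustration.

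A reader might infer that the ambiguity distorts the primary result, because FLT3-ITD patients contribute to event-free survival. The documents do not support that. Section 11.1 says that "this trial is not hypothesis-driven but rather estimation-driven", it plans no analysis by sorafenib exposure, and with fewer than one patient expected no effect on the estimate is shown. The sample size is untouched. This is a minor wording correction that merits making because it governs drug exposure in a child. I take no view on which of the two instructions is clinically right.

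**What to change.** Reconcile the two sentences for a first Grade 3 occurrence in section 6.11.1 so that restart and stop are exact complements, separated by one stated grade. The clinical team should choose that grade. Use the same wording in the bullet for a second Grade 2 occurrence; this is for consistency, since the conflict there is marginal. It would help to add a line saying whether a rash that has come down from Grade 3 to Grade 2 counts as a Grade 2 occurrence.

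The cost is a wording change to two bullets, plus the optional line. Sample size, endpoints and analyses are unaffected.

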***Treatment of sorafenib related Rash/Hand-foot syndrome**

- Patients who develop hand-foot syndrome may receive topical emollients (such as Aquaphor) as well as topical or oral steroids or antihistamines if appropriate. Hand foot syndrome may include skin pain without rash that impacts activities of daily living.
- Oral administration of vitamin B 6 (pyridoxine) can also be used for these patients - BSA < 0.5m²: 50 mg per day; BSA 0.5 - 1.0 m²: 100 mg per day; BSA 1.1 - 1.5 m²: 200 mg per day, and BSA > 1.5m²: 300 mg per day.

7.0 SUPPORTIVE CARE

7.1 General Guidelines

The following guidelines are intended to give general direction for optimal patient care and to encourage uniformity in the treatment of this study population. We will follow our institutional guidelines for management of hospitalization and discharge for these patients.

Hospitalization/Hospital Environment

Hospitalization following each course of chemotherapy is strongly recommended until the absolute phagocyte count (sum of the neutrophils, bands and monocytes) is rising for 2 successive days, and the patient is afebrile and clinically stable.

It is recommended that patients should be assigned to rooms with special air filtration systems such as high efficiency particulate air filters (HEPA) or clean-air rooms with constant positive pressure airflow if at all possible.

Central Venous Access

It is recommended that all patients have a double lumen central venous access line placed prior to the beginning of therapy.

Hyperleukocytosis and Metabolic Derangement

Patients with high peripheral blast counts (> 100,000/ μ L) may have increased problems related to metabolic abnormalities, bleeding, and hyperviscosity. Transfusion with packed red blood cells should be given very cautiously, since it may increase viscosity and increase the risk of leukostasis. In these patients, the platelet count should be maintained at least greater than 20,000/ μ L

Continuation of AML Therapy

AML therapy can proceed when there is documented evidence of response to antimicrobial therapy for infections complications, absence of fever or other signs or symptoms of infection, and other starting criteria have been met.

Nutrition

Active measures should be used to prevent weight loss of greater than 10% of pre-illness body weight. If possible, enteral feedings are preferred to parenteral.

Mucosal Evaluation and Care

Mucositis is expected and may be severe; liberal use of pain medications for this condition is encouraged. For patients with poor oral hygiene, consultation by dentistry is recommended prior to initiating therapy.

Suppression of Menstruation

Menstruating females may receive depo-injections or another suppressant during the entire course of this protocol per institutional standards.

Irradiation

Blood products should be irradiated following the current FDA guidelines found at:

<http://www.fda.gov/cber/gdlns/gamma.htm>

7.2 Infection Prophylaxis

Patients with AML are at a high risk for mortality and morbidity during therapy mainly due to infections. Therefore, patients require an aggressive approach to infection prevention and treatment as outlined below:

- Hospitalization as mentioned in Section 7.1

- Bacterial Prophylaxis

It is required that all patients except those receiving sorafenib receive broad spectrum gram –positive and gram-negative anti-bacterial prophylaxis at the start of each cycle of therapy and until they have met criteria for discharge as mentioned in section 7.1. Antibiotic can be decided by the treating institution, although levofloxacin is recommended.

- Pneumocystis jiroveci Prophylaxis

It is required that all patients receive prophylaxis for Pneumocystis jiroveci pneumonia during each cycle. Trimethoprim-sulphamethoxazole, pentamidine isethionate and dapsone are acceptable though trimethoprim-sulphamethoxazole is preferred.

- Fungal prophylaxis

Prophylactic anti-fungal therapy with voriconazole (<13 yrs), posaconazole (≥ 13 yrs) or micafungin is required until they have met criteria for discharge as mentioned in section 7.1.

Patients with an ANC < 500/ μ L (or < 1,000 / μ L and falling) and an oral temperature $> 38^{\circ}\text{C}$ twice in 12 hours or $\geq 38.3^{\circ}\text{C}$ once, should have empiric systemic antibiotics initiated immediately. Institutional guidelines as set forth for patients with AML which include guidelines for fever and neutropenia in AML patients, management of possible and documented fungal infections and pneumocystis prophylaxis will be followed.

8.1 EVALUATIONS/DATA TO BE ACCESSIONED

STUDIES TO BE OBTAINED	Baseline	Each Course of chemotherapy	End of therapy	Relapse/Refractory
History	X	---	---	---
Physical Exam	X	X	X	X
Vital Signs	X	X	X	X
Height, Weight, BSA	X	X	X	X
Performance status	X	X	X	X
CBC with differential, platelets	X	X	X	X
Liver Function – AST, ALT, Total and Direct Bilirubin, Total Protein, Albumin	X	X	X	X
Kidney Function – BUN, Creatinine	X	X	X	X
Electrolytes (Sodium, Potassium, Chloride, Calcium, Magnesium, Phosphorous) and Glucose	X	X	X	X
Chest X-ray and Pulse oximetry	X	---	---	X
ECHO and EKG	X	X Prior to each course	X	X
Bone marrow aspirate (BMA) and/or biopsy for morphology and flow cytometry to include CD33 expression	X	---	---	X
BMA for FLT3 testing	X	---	---	X
BMA for CD33 Genotype	X	---	---	---
BMA for genomic testing	X	---	---	X
Lumbar Puncture with cell count and cytospin	X	---	---	X
Imaging of chloroma –CT/MRI if applicable	X	---	---	X
BMA for MRD testing	--	X End of each course	X	--
Concomitant Medication Data	X	X	X	X
Adverse Event/Toxicity Monitoring		X	X	

